The licensed product literature for Isuprel[™] (Isoprenaline) lists administration in patients with tachyarrhythmias as a contraindication to use. This advice is applicable within the remit of the licensed uses for the drug and the expected environment of administration for those uses but is not directly relevant to our protocol. Our project administers isoprenaline to participants, some known to have a history of tachyarrhythmia, with the desired aim of induction of tachyarrhythmia in an environment where it is safe to do so. As described already, this is a common clinical use for the drug, albeit outside the licensed indications. There is an excellent safety profile demonstrated for use in this way and a large body of clinical experience which justifies the application in this study. Most importantly, if sustained tachyarrhythmia occurs during administration of isoprenaline, this protocol dictates the drug infusion be immediately discontinued. Coupled with the short duration of action of the drug, this means that isoprenaline will not be delivered during tachyarrhythmia and so adheres to the advice of the published product literature.

As discussed previously, one of the actions of isoprenaline is to increase heart rate and improve myocardial contractility with consequent increase in myocardial oxygen demand. Where there is coexistent obstructive coronary artery disease, this increase might lead to myocardial ischaemia with consequent angina pain for the subject and possible increase in the risk of myocardial infarction. There is published literature demonstrating the safety of using isoprenaline in the setting of obstructive coronary disease from its use in functional myocardial imaging(47)(48) and further evidence from a similar catecholamine; dobutamine with aggressive dosing regimens in the same setting(49). To safeguard participant safety, subjects with known obstructive coronary disease or active symptoms suggestive of angina will be excluded from enrolment. Given the available safety data, there is no requirement to rule out any other, undiagnosed obstructive coronary disease nor is there need to exclude subjects with non-obstructive disease.

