Although the actions of isoprenaline mean that its administration increases cardiac output, there is concern regarding increased myocardial strain in subjects with severe impairment of left ventricular function, active heart failure syndrome or severe valvulopathy. In addition there is concern regarding the potential to induce ventricular arrhythmias in high risk groups such as those know to have hypertrophic cardiomyopathy. All of these groups of participants have been excluded from enrolment with this study.

Induced episodes of atrial fibrillation

The goal of this study is to use a drug to precipitate an episode of the abnormal heart rhythm atrial fibrillation. In some cases the subjects have a known diagnosis of the arrhythmia, in some they will have never experienced the rhythm disturbance. Specific risks to be addressed from inducing an episode of atrial fibrillation include the potential to render that person more susceptible to atrial fibrillation in the future, the risks posed by being in the arrhythmia and any risk from iatrogenic restoration of sinus rhythm, most dramatically being the need for direct current cardioversion. In these participant groups, given the setting and duration of the episodes of atrial fibrillation being induced, we believe that we will be able to terminate atrial fibrillation and restore sinus rhythm if required in all subjects. We do not believe there is a risk of inducing a state of permanent atrial fibrillation.

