- Participants must have a pattern of symptoms and investigation results consistent with a diagnosis of paroxysmal atrial fibrillation

Group 2 – SVT Ablation Group

- Participants must have a history of arrhythmia with documented regular, narrow complex tachycardia available on either 12 lead ECG or ambulatory ECG monitor recording
- Participants must be listed to undergo an Electrophysiology study with a view to performing an ablation procedure
- Participants must go on to have an ablation procedure for either Atrio-Ventricular Re-entrant Tachycardia (AVRT) or Atrio-Ventricular Nodal Re-entrant Tachycardia (AVNRT) with a defined procedural endpoint

Group 3 – Atrial Flutter Ablation Group

- Participants must have a history of arrhythmia with 12 lead ECG documentation fulfilling prespecified criteria for diagnosis of common type (cavotricuspid isthmus dependent) atrial flutter
- Participants must be listed to undergo a cavotricuspid isthmus ablation for common type atrial flutter
- Participants must go on to have only a cavotricuspid isthmus ablation for common type atrial flutter
- Sustained bi-directional cavotricuspid isthmus block must have been demonstrated as the endpoint for the ablation procedure

Group 4 – Pulmonary Vein Isolation Group

- Participants must have a history of arrhythmia with 12 lead ECG or ambulatory ECG monitoring recordings documenting a diagnosis of atrial fibrillation
- Participants must be listed to undergo an ablation procedure for atrial fibrillation with the intent of the attending physician to perform pulmonary vein isolation alone as an ablation strategy
- Participants must be in sinus rhythm at the time that they enter the Cardiac Electrophysiology Laboratory for their ablation procedure.
- Participants must have an ablation procedure for atrial fibrillation and this must have involved only ablation to achieve pulmonary vein isolation
- Pulmonary vein isolation must have been demonstrated as the endpoint for the ablation procedure

Exclusion Criteria

All Participants in All Groups

- Allergy to Isoprenaline
- Any treatment with Amiodarone in the 3 months prior to ablation procedure
- Hypertrophic cardiomyopathy
- Suspected acute myocarditis
- Uncorrected, severe valvulopathy graded by transthoracic echocardiographic parameters
- An Acute Coronary Syndrome within the last 6 months
- Recent (within the last 6 months) or scheduled coronary revascularisation

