- Ongoing angina symptoms without investigations demonstrating the absence of myocardial ischaemia
- Left ventricular ejection fraction measured at <30%
- Symptoms of decompensated heart failure syndrome in the last 3 months
- Severe obstructive lung disease
- Pregnancy at the time of enrolment or a desire to become pregnant during the study period
- Women who are breastfeeding
- Reduced life expectancy not associated with cardiovascular disease (less than 1 year)
- Unable to provide informed consent

Group 1 – Paroxysmal Atrial Fibrillation Group

- Any past history of episode of persistent atrial fibrillation at the time of enrolment to the study
- Treatment with any antiarrhythmic agent within six half-lives of that agent from before an administration of the study drug infusion

Group 2 – SVT Ablation Group

- Any past history of atrial fibrillation documented on 12 lead ECG or ambulatory ECG monitor
- Any past history of atrial flutter documented on 12 lead ECG or ambulatory ECG monitor
- Characterisation of SVT as any arrhythmia other than ANRT or AVNRT
- Treatment with any antiarrhythmic agent within six half-lives of that agent from the ablation procedure (including intra-procedural use) with the exception of isoprenaline and adenosine

Group 3 – Atrial Flutter Ablation Group

- Characterisation of arrhythmia as any arrhythmia other than cavo-tricuspid isthmus dependent atrial flutter at the time of ablation
- Treatment with any antiarrhythmic agent within six half-lives of that agent from the ablation procedure (including intra-procedural use) with the exception of isoprenaline and adenosine

Group 4 – Pulmonary Vein Isolation Group

- Requirement for a more extensive ablation strategy than pulmonary vein isolation alone
- Intra-procedural treatment with any antiarrhythmic agent with the exception of isoprenaline and adenosine
- Treatment with any antiarrhythmic agent in the days before the ablation within six half-lives of that agent from the ablation procedure

Participant Information

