The minimum staff required to administer the infusion will include a registered nurse considered competent with administration of intravenous medications (as judged by the hospital trust at which the infusion is being delivered) and a licensed medical practitioner considered experienced in the field of cardiology and who is a certified Advanced Life Support provider.

Prior to administration of the study drug infusion, the study team will assess the participant regarding their potential suitability for use of antiarrhythmic medications in the event that atrial fibrillation which persists for greater than 10 minutes is induced.

The route of administration will depend on the situation in which the infusion is being administered. Where the infusion is being administered in a ward based environment, it is anticipated that the infusion will be delivered via a peripherally sited intravenous cannula usually sitting in an antecubital fossa vein. Where the infusion is being given in the Cardiac Electrophysiology Laboratory, it will usually be administered via a central venous sheath sited in the femoral vein. Standard aspetic technique associated with the administration of intravenous drugs will be applied in all settings to comply with local policy.

The study drug infusion will be delivered following a modified version of the scheme previously published by Morady and colleagues(30). As their study suggested an accelerating rate of induction up to the maximum dose delivered (20mcg/min), to allow for the potential effect of our study using the sulphate form of the drug rather than the hydrochloride and given the documented favourable tolerability profile of the infusion, we have elected to add a further dose increment to our protocol. This remains within the FDA approved dosing regimen for the drug.

The protocol will be..

- Infusion started at 5mcg per minute for 2 minutes
- Increased to 10mcg per minute for 2 minutes
- Increased to 15mcg per minute for 2 minutes
- Increased to 20mcg per minute for 2 minutes
- Increased to 25mcg per minute for 2 minutes
- Infusion is then stopped and subject is monitored over a 10 minute washout phase

Subjects will either follow the protocol to its completion or will reach one of the pre-defined infusion endpoints at which point the infusion will be stopped. These endpoints as described previously are..

Outcome after which infusion would be stopped

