 - The time from initiation of the infusion to the end of each episode of arrhythmia lasting less than 30 seconds

Concomitant Drug Therapy

In line with the product literature regarding Isoprenaline, epinephrine (adrenaline) should not be administered simultaneously with the study drug infusion due to the risks of the combined actions of isoprenaline and epinephrine. Likewise potent inhalational anaesthetic agents such as halothane will be avoided during the delivery of the study drug infusion due to the potential for sensitisation of the myocardium to the effects of sympathomimetic agents.

Study Procedure - Protocol Part A

Subjects recruited to Part A of the study will be required to make a minimum of two and maximum of three visits to the hospital for that part of the study. They will be required to attend for administration of an open label, isoprenaline study infusion on two separate occasions at least two weeks apart. The paroxysmal atrial fibrillation group of subjects will be enrolled to this part of the study.

• Part A - Contact 1 - Enrolment Visit

Following a statement of interest to be involved in the study and satisfactory screening with regard to inclusion and exclusion criteria, the subject will be invited to attend for an enrolment visit. At this contact between the potential participant and investigators, the research team will offer further explanation of the study, answer any questions the recruit has and ensure that the individual still wishes to take part in the study and that they still conform to the inclusion / exclusion criteria. The participant will have been given or sent a copy of the relevant Participant Information Sheet prior to this contact. If suitable and willing, they will be enrolled into the study having given written informed consent to do so.

Once the participant is enrolled in the study, the investigators will take baseline demographics and medical information. Baseline demographics will include age, sex, marital status, occupation and ethnic group. Baseline medical information will include current medical diagnoses, duration of those diagnoses, duration of symptoms relating to any diagnoses, number of episodes of symptoms in the month prior, NYHA class, CHADS₂ score, CHA₂DS₂ VASc score, HAS BLED score, Framingham risk of atrial fibrillation score, alcohol consumption, smoking status and exercise / activity history.

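### The safety case excludes known obstructive coronary disease, but no eligibility criterion does, so stable asymptomatic disease passes screening for isoprenaline at up to 25 mcg/min

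*Protocol*

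**What the plan says.** In the Protocol, the Administration of Isoprenaline subsection of Potential Risks and Benefits for Study Subjects explains that the drug raises myocardial oxygen demand. With coexisting obstructive coronary disease this may cause ischaemia, angina and possibly infarction. After citing safety literature, it commits to a safeguard: "To safeguard participant safety, subjects with known obstructive coronary disease or active symptoms suggestive of angina will be excluded from enrolment". It then marks the limit of that commitment: "there is no requirement to rule out any other, undiagnosed obstructive coronary disease nor is there need to exclude subjects with non-obstructive disease". The next paragraph names severe left ventricular impairment, active heart failure, severe valvulopathy and high-risk groups such as hypertrophic cardiomyopathy, and closes: "All of these groups of participants have been excluded from enrolment with this study".

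Under Exclusion Criteria, All Participants in All Groups, there are three coronary lines:

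- one on past events: "An Acute Coronary Syndrome within the last 6 months"
- one on procedures, which removes anyone revascularised in the preceding 6 months or listed for it
- one on symptoms: "Ongoing angina symptoms without investigations demonstrating the absence of myocardial ischaemia"

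The enrolment visit for each part (Part A Contact 1, Part B Visit 1) follows "satisfactory screening with regard to inclusion and exclusion criteria". The last step of the Infusion Protocol reads "Increased to 25mcg per minute for 2 minutes".

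**The concern.** The risk section gives two separate grounds for exclusion, joined by an 'or': known obstructive disease, and active anginal symptoms. The eligibility list turns the second into a criterion but not the first. Recent events, recent or planned procedures and current symptoms describe unstable, recently treated or symptomatic disease. They do not describe a diagnosis of obstructive disease that is currently quiet.

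Participant safety is at stake, not inference. The Protocol says participants are not expected to benefit directly from the drug, and it identifies ischaemia and infarction as the hazard in this population. A committee reading the risk section would believe that a protection is in place which the screening list does not provide.

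**Working it through.** No sample size, power or event rate enters this point, so the check is a comparison of texts, with one small dose calculation.

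**1. What the risk section requires.** It excludes known obstructive disease. It waives only undiagnosed obstructive disease and non-obstructive disease. Known obstructive disease is therefore out whether or not symptoms are present.

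**2. Test case against the list.** Take a person with known obstructive coronary disease, no acute coronary syndrome and no revascularisation in the past 6 months, none scheduled, and no current angina.

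| Coronary criterion (all groups) | Met? |
|---|---|
| Acute coronary syndrome in past 6 months | No |
| Revascularisation in past 6 months, or scheduled | No |
| Ongoing angina not cleared of ischaemia | No |

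The person is excluded by the risk section and passes the list.

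**3. Does other text close the gap?**

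- The inclusion criteria and the group-specific exclusions for Groups 1 to 4 do not mention coronary disease.
- The assessment before each infusion (Infusion Protocol) concerns suitability for antiarrhythmic drugs only.
- The removal rules (Reasons for Discontinuation of Subject's Participation in Study) act on failure of a listed criterion, or on anaphylaxis, chest pain or ischaemic ECG features during the infusion. The first leads back to the same list, and the second applies only after exposure.

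**4. Cardiac groups named in the risk section against the list.**

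| Named in the risk section | Line in the all-group list |
|---|---|
| Known obstructive coronary disease | None |
| Active anginal symptoms | Ongoing angina not cleared of ischaemia |
| Severe left ventricular impairment | Ejection fraction below 30% |
| Active heart failure | Decompensated symptoms in past 3 months |
| Severe valvulopathy | Uncorrected severe valvulopathy |
| Hypertrophic cardiomyopathy | Hypertrophic cardiomyopathy |

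Five of the six have a counterpart, some of them narrower than the risk section. Known obstructive disease has none, which looks like an omission.

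**5. Exposure of an affected person.** The Infusion Protocol has five steps of 2 minutes each:

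- dose per completed infusion = 2 min × (5 + 10 + 15 + 20 + 25) mcg/min = 2 × 75 = 150 mcg
- two planned infusions = 2 × 150 = 300 mcg
- peak rate = 25 mcg/min

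In Part A every participant is scheduled for two isoprenaline infusions. In Part B, with 1:1 randomisation, only the isoprenaline arm receives the drug.

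**The case against.** The strongest reply is that the risk section is itself Protocol text, so an investigator who follows the whole document would exclude this person, and the three coronary lines are simply the working form of the commitment. The list does narrow the risk section elsewhere, for example on heart failure and valve disease. That reading is fair for the angina clause, where the difference is a minor point of wording. It fails for known obstructive disease, because it leaves the first half of the commitment with no effect. Screening is also tied to the criteria, so the list is what decides enrolment in practice.

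A second reply is that the risk is limited. The Protocol cites published safety data in obstructive disease and on that basis accepts undiagnosed disease. It also provides continuous ECG, blood pressure every minute, a physician certified in Advanced Life Support, a defibrillator, and stopping for ischaemic ECG changes or severe chest tightness. All of this stands and lowers the residual risk. But these measures act once the drug is running, and the Protocol, having weighed the same literature, still chose exclusion as the safeguard.

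Three smaller points are accepted. The sentence saying that all of these groups are excluded refers most naturally to the groups in its own paragraph, so it shows the intent of the section but adds nothing on coronary disease. The tally of six treats an open-ended arrhythmia category as one group. The 300 mcg sum means little for a drug with a brief action, and it is not the study maximum, since one person may join both parts. The peak rate is the figure that matters.

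**Conclusion.** The point holds: the Protocol contradicts itself on eligibility. The risk section excludes known obstructive coronary disease, while the list used for screening admits it when it is stable, currently free of angina, and without an acute coronary syndrome or revascularisation in the past 6 months or a scheduled revascularisation. An affected person given isoprenaline is exposed to up to 25 mcg/min and 150 mcg per completed infusion.

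The number of such people cannot be derived, because the Protocol gives no prevalence of known stable disease in its groups. The subset may be small. No bias in the outcome data is claimed. The conclusion assumes only that sites screen on the criteria, as both enrolment sections state. It must be corrected because it concerns participant safety and the correction is simple.

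**What to change.** Add to Exclusion Criteria, All Participants in All Groups a line such as: 'Known obstructive coronary artery disease', with a working definition. State how disease revascularised more than 6 months ago is to be handled, since the present list admits it without comment. In the same amendment, align the angina wording of the risk section with that of the criterion.

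If the investigators do intend to enrol stable, asymptomatic obstructive disease, leave the list as it is, amend the risk section to say so, and justify it from the safety data it cites.

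The cost is a short protocol amendment needing the sponsor, ethics, regulatory and Trust R&D approvals set out under Regulatory review, plus, if the exclusion is added, a probably small loss of eligible patients. Design, sample size and analysis do not change.
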